The inflammatory response in the posterior chamber leads to protein condensation in the vitreous humor, making it difficult to visualize the fundus and therefore to characterize the degree of damage to the retina and its vasculature.

In 80% of patients, retinal vessels cannot be seen, and ultrasound is necessary to check for the initial presence of tractional membranes or retinal detachment. To this

Protocol ID: CVAE 01

day, the role that this increase in proteins, increased permeability, and blood stasis (Secondary to significant local inflammation) may have on the retinal vasculature remains unclear.

Chronic degenerative diseases, through their respective pathophysiological processes, condition a systemic pro-inflammatory state. In cases where they exist as an underlying pathology, they can contribute to the presence of incipient vascular damage, making individuals more susceptible to damage to the microcirculation in ocular infectious processes, such as endophthalmitis.

The clinical evolution of endophthalmitis depends on the intravitreal release of inflammatory cytokines, which promote neutrophil aggregation, leading to a variable degree of tissue necrosis and resulting in the presence of vitritis, perivascular exudate, vessel sheathing, diffuse patchy hemorrhages, phlebitis/periphlebitis, and occlusion of arteries proximal to the macula. However, these changes have been described as nonspecific; the main factor related to their presentation is unknown, and there is the possibility of undescribed damage (such as the presence of peripheral vascular lesions)

Imaging techniques have undergone enormous advances in recent years, drastically improving the knowledge of the anatomy, functional, and metabolic state of the retina. (2) Optical coherence tomography (OCT) allows non-invasive cross-sectional imaging of the retina and choroid. Fluorescein angiography is the study of choice for the evaluation of the vascular system, and wide-field fundus photographs provide an overview of the integrity of the retina and its vasculature (7-9)

Nowadays, there are no studies that describe vascular changes associated with endophthalmitis. However, when the previously mentioned techniques are used in combination, they can be used to evaluate the response to treatment and demonstrate ischemic changes or early vascular damage (11-14). Thus opening the possibility to implement early therapies that lead to a better final visual prognosis (12-14)

Protocol ID: CVAE 01

Justification: The implementation of multimodal imaging studies during the diagnosis and follow-up of patients with endophthalmitis may help to identify, characterize, and differentiate between changes associated with host immune response, drug toxicity, or ischemia, thus opening the possibility of the implementation of early treatments leading to a better final prognosis

Problem statement

Enophthalmitis is a serious condition that can result in both anatomical and functional consequences for the eye. Despite being an inflammatory condition of the eye, little is known about the vascular changes that occur secondary to endophthalmitis. For this reason, it has been decided to investigate whether angiographic changes correlate with visual prognosis in the short or medium term, as well as the comorbidities associated with each case. Do angiographic vascular changes correlate with visual prognosis?

2.1. **Objectives and hypotheses**

2.1.1.1. **General Objectives:** To describe and investigate vascular changes associated with exogenous endophthalmitis, as well as to create a photo library where they are evidenced

2.1.1.2. **Specific Objectives**

- 1. To demonstrate the presence or absence of perivasculär exudate, vessel sheathing, phlebitis/periphlebitis, diffuse or localized hemorrhages, arteriovenous shunts, vascular closure zones, and neovessels, as well as their pattern of location (in the central or peripheral region of the retina) by means of fundus photography, optical coherence tomography, and fluorescein angiography
-
- 2. To identify and correlate the presence of incipient vascular damage that could make the microcirculation more susceptible to damage during ocular infectious processes in patients with significant personal pathological history
-

Protocol ID: CVAE 01

- 3. To describe vascular changes according to their probable etiology (ischemic, drug-mediated toxicity, and host immune response) using fundus photography, optical coherence tomography, and fluorescein angiography

2.1.2. Hypothesis

2.1.3. Null hypothesis

- The incidence of vascular changes (exudates, hemorrhages, areas of capillary closure) is greater than 50% of cases, regardless of the pathogen or the treatment indicated

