2.1.3.1. Alternate hypothesis

- The incidence of vascular changes (exudates, hemorrhages, areas of capillary closure) will be less than 50% of the cases, regardless of pathogen or treatment indicated.

3. Study design

According to the moment at which the information is collected.

- Prospective - a study where the information will be collected in the future, after the beginning of the research

3.1. According to the number of times the primary variable of interest is measured or determined.

- Longitudinal.- The primary variable of interest is measured more than once over time

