3.2. According to the researcher's interference in the phenomenon being analyzed

- Observational.- The researcher only describes or measures the phenomenon

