3.3. According to the analysis of the study population(S)

- Descriptive.- The researcher only has a population and describes it

4. Methodology

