4.2 Description

Patients who meet the inclusion criteria will be invited to participate in the study, who will have a history of endophthalmitis and who have clear media (clear cornea, anterior chamber cellularity + or less, vitritis + or less), one week and one month after meeting the resolution criteria established by the Mexican Endophthalmitis Group.

After signing the informed consent form

A comprehensive ophthalmologic examination will be performed, including assessment of visual acuity and intraocular pressure.

A fluorescein angiography will be performed one week after meeting resolution criteria, and one month later.

Fluorescein 10% (10mg/ml) will be injected intravenously through a peripheral line.

Fundus photographs will be taken with the Clarus 700 equipment

The pictures will be analyzed in different phases and in different areas

The changes will be compared at different times, one week after meeting the resolution criteria and one month later

Consecutive recruitment will be done

Protocol ID: CVAE 01

The data will be stored in a table in Excel 2007

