Based on this projection, we decided to use the **sample size formula for proportion estimation**, as our working hypothesis suggests that the **incidence of vascular changes** will be **greater than 50%**.

The sample size was calculated using an **online proportion estimation calculator**:

<https://www.calculator.net/sample-size-calculator.html?type=1&cl=95&ci=5&pp=50&ps=86&x=Calculate>:

Result

Sample size: **71**

This means 71 or more measurements/surveys are needed to have a confidence level of 95% that the real value is within $\pm 5\%$ of the measured/surveyed value.

Confidence Level:	95%	
Margin of Error:	5 %	
Population Proportion:	50 %	Use 50% if not sure
Population Size:	86	Leave blank if unlimited population size.

Calculate  **Clear**

A total of **71 patients** were included to achieve a **95% confidence interval**, with a **5% margin of error**, a **population proportion of 50%**, and a **total population size of 86 patients**.

We will calculate **measures of central tendency** (mean, median, and mode). **Chi-square tests** will be used for qualitative variables.

Data will be analyzed using the **SPSS software, version 25**.

Organization

Human Resources:

- Retina specialists affiliated with the Retina Service
- Medical intern completing social service
- Retina fellows
- Nursing staff

Protocol ID: CVAE 01

Material Resources:

- Computer
- **HRA Spectralis Heidelberg OCT**, Serial #Spec-CAM-15095-S3610, Magnification 30°, Software version 7.0.6.0
- **Clarus 700 Zeiss**, Serial #CL700-73467, Software version 1.1.2.59261, Digital Camera Magnification 133°
- Dye
- Needles
- Plastic catheters
- Vials of fluorescein

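### The null and alternative hypotheses (sections 2.1.3 and 2.1.3.1) are reversed relative to the working hypothesis in the sample size section, and an incidence of exactly 50% falls under neither

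*Protocol*

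**What the plan says.** Three statements in the protocol bear on the direction of the hypothesis.

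- Section 2.1.3 gives the null for the incidence of vascular changes: "exudates, hemorrhages, areas of capillary closure) is greater than 50% of cases".
- Section 2.1.3.1 gives the alternative: "exudates, hemorrhages, areas of capillary closure) will be less than 50% of the cases".
- The sample size text in section 5.2 justifies its choice of formula "as our working hypothesis suggests that the incidence of vascular changes will be greater than 50" percent.

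The setting is descriptive. Section 3.2 classifies the study as "Observational.- The researcher only describes or measures the phenomenon" and section 3.3 as "Descriptive.- The researcher only has a population and describes it". For the sample size, "we decided to use the sample size formula for proportion estimation", with 95% confidence, a margin of ±5 points, a planning proportion of 50% and a population of 86; the result is 71. The only test named is in the same section: "Chi-square tests will be used for qualitative variables". No one-sample test against 50%, significance level or power is given.

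**The concern.** Rejecting a null hypothesis supports the alternative; failing to reject it supports nothing. With the pair as written, the only claim that a directional test could establish is an incidence below 50%, the opposite of what the investigators expect. Their expectation could only be left standing, and an imprecise result would leave it standing most easily. A reader who takes the hypotheses literally could then report an inconclusive proportion as agreeing with the protocol.

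Both inequalities are strict, so 50% itself is in neither hypothesis. That value is also the planning proportion in section 5.2, and it is the boundary at which the error rate of a one-sided test would be fixed.

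**Working it through.** **1. Direction of the statements**

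| Place | Role | Incidence |
|---|---|---|
| 2.1.3 | Null | > 50% |
| 2.1.3.1 | Alternative | < 50% |
| 5.2, sample size | Working hypothesis | > 50% |

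The working hypothesis matches the null. Exactly 50% is in no row. Nothing else in the protocol reconciles the three.

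**2. Does the sample size depend on this?** Inputs from section 5.2: 95% confidence, e = 0.05, p = 0.50, N = 86.

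- n0 = z² p(1−p)/e² = 1.96² × 0.25/0.0025 = 384.15 (unrounded z)
- n = n0/(1 + (n0 − 1)/N) = 384.15/(1 + 383.15/86) = 70.42, rounded up to 71

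The protocol's 71 is reproduced. No hypothesis enters the formula, so correcting the direction leaves it at 71.

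**3. Which results would be inconclusive about 50%?** Exact (Clopper-Pearson) 95% intervals, n = 71:

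| Result | Estimate | 95% interval |
|---|---|---|
| 26/71 | 36.6% | 25.5% to 48.9% |
| 27/71 | 38.0% | 26.8% to 50.3% |
| 35/71 | 49.3% | 37.2% to 61.4% |
| 37/71 | 52.1% | 39.9% to 64.1% |
| 44/71 | 62.0% | 49.7% to 73.2% |
| 45/71 | 63.4% | 51.1% to 74.5% |

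The interval contains 50% from 27/71 to 44/71, which is 44 − 27 + 1 = 18 counts. Of these, 27 to 35 (nine counts) have an estimate below 50%, yet none would displace the written null of more than 50%.

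These intervals use no finite-population correction. The 86 is 57 cases in 8 months scaled to a year (57/8 × 12 = 85.5), and section 4.2 says "Consecutive recruitment will be done". It is a projected count, not a fixed population being sampled.

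**4. Illustration with an assumed test.** The protocol names no test or level. Assume an exact one-sided binomial test of the written null at the boundary p = 0.5.

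- Level 2.5%: P(X ≤ 26) = 0.0160 and P(X ≤ 27) = 0.0284, so reject at 26 or fewer. Non-rejection P(X ≥ 27) is 0.904 at a true 45% and 0.675 at a true 40%.
- Level 5%: P(X ≤ 28) = 0.0480, so reject at 28 or fewer. Non-rejection P(X ≥ 29) is 0.794 at a true 45%.

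So with a true incidence below one half, the written null of more than 50% would usually survive.

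**5. What the corrected reading requires.** If support means that the lower exact 95% limit exceeds 50%, the threshold is 45/71. P(X ≥ 45) is 0.016 at a true 50%, 0.325 at 60%, 0.663 at 65% and 0.909 at 70%. The interval method matters at the edge: for 44/71 the lower limit is 49.7% with the exact interval and 50.3% with Wilson.

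**The case against.** The strongest reply is that no planned result depends on the labels. The study describes and estimates, the 71 is precision-based, and an estimate with its interval reads the same whichever statement is called the null. The non-rejection rates come from a test that the protocol does not contain. If the named chi-square were applied against 50%, it would be two-sided and indifferent to the labels. All of this stands. It limits the point to the stated hypotheses and how a result is read against them, and the rates in step 4 are illustration only.

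A second reply concerns size. With the protocol's own finite-population correction (normal approximation, variance factor (86 − 71)/85 = 15/85), the 95% interval contains 50% only from 33/71 to 38/71, six counts, and the lower limit first passes 50% at 39/71 (54.9%, 50.1% to 59.8%). The arithmetic is right, but it treats a projected annual count as the complete target population. The reversal of the hypotheses is the same under either calculation.

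Two smaller replies also have some force. With 71 patients, an odd number, no observed proportion can equal 50%, so that gap is formal. The choice of interval could be left to an analysis plan. Neither removes the contradiction, which lies in hypotheses that the protocol itself fixes.

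**Conclusion.** The concern holds. The protocol's only formal hypotheses run opposite to its working hypothesis and omit the boundary value, and nothing in the text resolves this. Followed literally, they let the expected result stand by non-rejection but never be positively supported.

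The consequence is a risk of misinterpretation, not a planned analysis error, and neither the sample size nor data collection is affected. The width of the inconclusive zone (18 counts) assumes 71 evaluable patients, an exact binomial interval and no finite-population correction. The contradiction itself rests on no assumption. It should be corrected before results are interpreted, so that the direction is not chosen after the data are seen.

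**What to change.** Do one of two things:

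- restate section 2.1.3 as H0: incidence of vascular changes ≤ 50%, and section 2.1.3.1 as H1: incidence > 50%; or
- delete the pair, which suits a descriptive study, and keep the working hypothesis as a stated expectation.

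In either case, report the proportion with a two-sided 95% confidence interval, name the interval method, and describe the working hypothesis as supported only if the lower limit exceeds 50%.

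The cost is a change of text. The price in interpretation is that a borderline result such as 37/71 can no longer be read as support. With the exact interval, the chance of support is about 33% at a true 60%, 66% at 65% and 91% at 70%.

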2.1.3.1. Alternate hypothesis

- The incidence of vascular changes (exudates, hemorrhages, areas of capillary closure) will be less than 50% of the cases, regardless of pathogen or treatment indicated.

3. Study design

According to the moment at which the information is collected.

- Prospective - a study where the information will be collected in the future, after the beginning of the research

3.1. According to the number of times the primary variable of interest is measured or determined.

- Longitudinal.- The primary variable of interest is measured more than once over time

3.2. According to the researcher's interference in the phenomenon being analyzed

- Observational.- The researcher only describes or measures the phenomenon

3.3. According to the analysis of the study population(S)

- Descriptive.- The researcher only has a population and describes it

4. Methodology

4.1. Place and duration

The population will be patients of the retina and vitreous service of Asociación para Evitar la Ceguera en México, attended from July to December 2024, who have a complete clinical record (age, sex, pathological personal history, non-pathological personal history, heredofamilial history, ophthalmologic history, allergies, medications, ophthalmologic examination with visual acuity, intraocular pressure at each visit), signed informed consent and with a history of exogenous or endogenous endophthalmitis with clear resolution criteria and clear means one week and one month after meeting the resolution criteria to be able to perform fluorescein angiography at both visits.

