4.2. Inclusion criteria

- **Patients with a history of endophthalmitis**
- Diagnosis of Endophthalmitis
 - Clinical symptoms: Pain, decrease in visual acuity, anterior chamber cells and/or vitreous turbidity, corneal edema, conjunctival hyperemia
 - Laboratory studies: B-mode USG and or positive culture
- Patients who meet the endophthalmitis resolution criteria of the Mexican Endophthalmitis Study Group
- Patients with previously signed informed consent

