4.3. Exclusion criteria

- Patients who have not signed the informed consent
- Patients under 18 years.
- Patients with endophthalmitis who do not meet the resolution criteria of the Mexican Endophthalmitis Study Group

Protocol ID: CVAE 01

5. Study variables

Variable name	Independent or Dependent	Nominal /ordinal/ dimensional	Unit of measurement	Measurement instrument	Time of measurement
Visual acuity	Independent	Ordinal	logMAR	Snellen Chart	At diagnosis, one week after resolution, and one month after
Vascular changes in FAG (Areas of capillary closure)	Independent	Ordinal	Disc areas	Fluorescein angiography	one week after resolution and one month after
Vascular changes in FAG (Periphlebitis)	Independent	Ordinal	Presence or absence	Fluorescein angiography with fluorescein	one week after resolution and one month after
Vascular changes in FAG (Hejorrhages on staining)	Independent	Ordinal	Presence or absence	Fluorescein angiography with fluorescein	one week after resolution and one month after
Vascular changes in FAG (Areas of leakage)	Independent	Ordinal	Disc areas	Fluorescein angiography	one week after resolution and one month after

Isolated body	Independent	Ordinal	Presence or absence of microorgan	Medium Culture	Single. When an organism grows in the culture
---------------	-------------	---------	-----------------------------------	----------------	---

Protocol ID: CVAE 01

			ism in culture		
--	--	--	----------------	--	--

Age	Independent	Dimensional	Years completed	Interrogation	Visit 1
-----	-------------	-------------	-----------------	---------------	---------

Sex	Independent	Nominal, dichotomic	Female/ Male	Tab from the collection	Unique
-----	-------------	---------------------	--------------	-------------------------	--------

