The structures to be evaluated include the **optic nerve, retina, retinal vasculature**, and transparency of the **posterior segment media**, among others. This procedure will be performed **at all study visits** by the designated clinical team.

Spectral-Domain Optical Coherence Tomography (SD-OCT)

OCT imaging will be performed using the HRA Spectralis Heidelberg, Serial # Spec-CAM-15095-S3610, with a Magnification of 30° and Software version 7.0.6.0. This will aid in evaluating the retinal condition, including central macular thickness and central retinal volume (commonly referred to as macular cube volume in OCT terminology).

A technician or delegated personnel may carry out this procedure, and will be performed at all study visits.

Fundus Photography and Fluorescein Angiography

Fundus imaging will be performed using the **Clarus 700 Zeiss**, Serial #CL700-73467, Software version 1.1.2.59261, Digital Camera Magnification 133°. Images of the **posterior pole and retinal periphery** will be captured, providing a comprehensive view of retinal integrity, the optic nerve, and its vasculature.

Fluorescein angiography will be performed subsequently to evaluate **associated vascular changes**. The patient must undergo an **8-hour fast** and have **pupillary dilation with TP Ofteno® (tropicamide 5% / phenylephrine 0.8%)**. The procedure involves preparing the patient with aseptic technique for an **intravenous injection of fluorescein dye** in an upper limb, followed by imaging with a fundus camera.

It is not essential to use a device of a specific brand or model, as long as a system with **equivalent specifications** is used consistently for the **same patient throughout the study**. The procedure may be performed by a **technician or**

Protocol ID: CVAE 01

delegated personnel, and will be conducted **at all study visits** (7 days and 1 month after meeting the inactivation criteria for endophthalmitis).

Sample size

A review of hospital medical records was conducted to identify patients diagnosed with **endophthalmitis** from **February 2024 to September 2024**, resulting in a total of **57 patients**.

Considering this data was collected over 8 months, a **proportional extrapolation** was made to estimate the number of cases in a **12-month calendar year**, yielding approximately **86 patients**.

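### The general objective covers exogenous endophthalmitis only, but section 4.1 admits endogenous cases and route of infection is not a study variable, so the planned incidence does not match the objective

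*Protocol*

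**What the plan says.** The sections that define whom the study is about do not agree.

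- **General objective (2.1.1.1):** "To describe and investigate vascular changes associated with exogenous endophthalmitis". This is the only general objective, and it names one route.
- **Population (4.1):** patients with "signed informed consent and with a history of exogenous or endogenous endophthalmitis with clear resolution criteria". Endogenous disease is admitted by name.
- **Inclusion criteria (4.2):** "Patients with a history of endophthalmitis", with no mention of route.
- **Exclusion criteria (4.3):** missing consent, age under 18, and "Patients with endophthalmitis who do not meet the resolution criteria of the Mexican Endophthalmitis Study Group". None of these removes endogenous cases.
- **Null hypothesis (2.1.3):** "The incidence of vascular changes (exudates, hemorrhages, areas of capillary closure) is greater than 50% of cases, regardless of the pathogen". The alternate hypothesis (2.1.3.1) likewise makes no distinction by route.
- **Sample size (5.2):** "A review of hospital medical records was conducted to identify patients diagnosed with" endophthalmitis found 57 patients in 8 months. This was scaled to 86 a year, from which 71 was derived. Route is not stated.
- **Study variables (5):** visual acuity, four angiographic findings, culture isolate, age and sex. The nearest entry to route is the culture result, timed as "Single. When an organism grows in the culture". It records whether an organism grew, not how infection reached the eye.

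**The concern.** The study's main planned quantity is the incidence of vascular changes, to be judged against 50%. Section 4.2 (Description) specifies consecutive recruitment, so every eligible endogenous case enters the numerator and denominator. The result will describe a mixture of the two routes, while the general objective asks about exogenous disease. If vascular changes are more or less common in endogenous cases, the pooled figure departs from the one the objective calls for. Because route is not a planned variable, the report cannot be relied on to show by how much.

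The rest of the protocol does not reveal which population was meant. The background supports the use of imaging to detect ischemic or early vascular damage by citing references 11 to 14, whose titles all concern endogenous endophthalmitis. References 2 to 7, by their titles, concern postoperative or cataract-related disease. The rationale draws on both routes, so the word in the objective cannot simply be assumed to be a slip.

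**Working it through.** **Inputs from the protocol (5.2):** 57 patients in 8 months; population N = 86; 95% confidence; 5-point margin; assumed proportion 50%; stated sample size 71.

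**Input not in the protocol:** the endogenous share s. I take 10% and 20% as assumptions.

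**1. Reproduce the stated figure.**
- 57 × 12/8 = 85.5, rounded to 86.
- Without a population correction: n0 = 1.96² × 0.25 / 0.05² = 384.16.
- With the finite population correction: n = 384.16 / (1 + 384.16/86) = 70.3, rounded up to 71. The variant with n0 − 1 in the denominator gives 70.4, also 71.

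The 71 reproduces. It applies to endophthalmitis of unstated route.

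**2. Effect of pooling on the incidence.**
- Pooled incidence = (1 − s) × p_exo + s × p_endo.
- Pooled minus exogenous = s × (p_endo − p_exo).
- For a shift equal to the 5-point margin, the rates must differ by 5/0.10 = 50 points at s = 10%, or 5/0.20 = 25 points at s = 20%.
- The shift is zero if the rates are equal or s = 0.

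A smaller shift can still matter near 50%. Purely as illustration, assume p_exo = 45% and p_endo = 80%. The pooled incidence is then 0.90 × 45 + 0.10 × 80 = 48.5% at s = 10%, and 0.80 × 45 + 0.20 × 80 = 52.0% at s = 20%. With these assumed rates the pooled figure exceeds 50% once s passes 5/35, about 14%.

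**3. Effect of restricting to exogenous cases.** N and n are 86 and 71 multiplied by (1 − s) and rounded. The half-width at 50% is 1.96 × √[(0.25/n) × (N − n)/(N − 1)], and the required n is 384.16 / (1 + 384.16/N).

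| Assumed endogenous share | Exogenous n of N | Half-width (points) | n needed for 5 points |
|---|---|---|---|
| 0% (as planned) | 71 of 86 | 4.89 | 70.3 → 71 |
| 10% | 64 of 77 | 5.07 | 64.1 → 65 |
| 20% | 57 of 69 | 5.45 | 58.5 → 59 |

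If 71 patients of both routes were enrolled, the exogenous subset would fall short of the 5-point margin by 1 patient (65 − 64) or 2 patients (59 − 57).

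**The case against.** The strongest reply is that one word in one sentence is out of line. The problem statement, specific objectives, hypotheses, population, eligibility lists and sample size do not restrict to exogenous disease. The general objective sets no incidence; the hypotheses do, and they match eligibility and the 86/71 calculation. This is right as far as it goes, and it makes widening the objective the easier repair. It does not remove the contradiction: the objective names one route and section 4.1 expressly names two.

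A second reply is that the variables table is not a full list of what is collected. Intraocular pressure and the OCT measures also have no row, and section 4.1 requires a complete record with pathological and ophthalmologic history, from which route may be recoverable. That stands: it would be too much to say the two groups could never be separated. But recovery is possible rather than planned. A breakdown by route could be left to a statistical analysis plan, but such a plan cannot make the objective and the population definition agree.

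A third reply is that the numerical effect is small or unknown. This also stands. The loss of precision is a fraction of a point on the protocol's own basis. Without the finite population correction, the half-width is about 11.6 points for 71 patients and 12.3 for 64, so the loss of precision from restricting is minor beside general sampling error. The 45%/80% illustration has no basis in the protocol. These points limit the size of the concern but do not answer it.

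**Conclusion.** The concern holds. The protocol's current text states an exogenous objective and enrols, hypothesises about and sizes for endophthalmitis of either route, without planning to record route. Confidence in this inconsistency is high.

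Its effect on the result cannot be sized from the protocol and may be nil. It depends on an endogenous share and route-specific incidences that are not given. At the assumed shares of 10% and 20%, only large differences between routes (50 and 25 points) would move the incidence by as much as the planned margin. The precision figures accept the protocol's finite population of 86 and assume that 71 patients are reached. The point should be corrected because the target of the main estimate is ambiguous and the correction costs little, not because a definite bias has been shown.

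**What to change.** Reconcile the general objective, section 4.1 and the inclusion and exclusion criteria on one target population, and add route of infection (exogenous or endogenous) to the variables table, taken from the history already required. Which population is intended is for the sponsor to say.

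- **If both routes are kept**, as the hypotheses and the 86/71 calculation already imply, widen the general objective and report the incidence overall and by route. The cost is a wording change and one data column, with no loss of precision for the overall figure. The endogenous estimate would be very imprecise: about 7 or 14 patients at the assumed shares, or 1.96 × √(0.25/7) = 37 and 1.96 × √(0.25/14) = 26 points either way at 50%. It should be presented as descriptive only.
- **If only exogenous cases are intended**, restrict eligibility or the analysis set to them, repeat the record count for exogenous cases, and restate the 86 and 71. At the assumed shares the requirement would be 65 of 77 or 59 of 69.
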